Exploratory objectives will include evaluation of the safety and efficacy of atezolizumab in patient subgroups differentiated by: presence or absence of CNS metastases at baseline; ECOG performance status; histological subtype; history of or current autoimmune disease; and prior anticancer treatment. Other exploratory and PRO outcomes will include objective response rate and progression-free survival 2 (PFS2) following start of new anticancer therapy, HR QoL as measured on the EORTC LQ-LC13, health utility score as measured on the EQ-5D-5L instrument, and expression of PD-L1 protein and cancer-related genes in tumor samples obtained before treatment. Finally, exploratory biomarkers may be assessed in tissue to assist in the potential development of new diagnostic assays and to assess biomarkers in terms of prognosis, response/resistance and safety.

Following discontinuation of study treatment, safety assessments will be conducted for 30 days after the last study drug administration or until initiation of other anti-cancer therapy (whichever occurs first). Thereafter, follow-up information on disease progression (unless this has already occurred), anti-cancer therapy and survival will be collected via telephone contact, patient medical records, and/or clinic visits approximately every 3 months until death, loss to follow-up, end of study (30 months after last patient in), patient withdrawal or study termination by the Sponsor, whichever occurs first. In addition, irAEs, SAEs and AESIs will be collected as described in Section [5.4.2](#).

In those patients for whom tumor assessments are performed as part of local clinical practice and are available for report after PD or atezolizumab treatment discontinuation, overall response rate (ORR) and progression-free survival (PFS) will be assessed from the first date of the new anticancer therapy to the end of the study. These data will be used in an exploratory fashion to assess whether prior atezolizumab treatment positively influences response to subsequent anticancer therapies.

An Independent Data Monitoring Committee (iDMC) will be established to review all AEs, irAEs, SAEs, AESIs and other cumulative safety data.

A Schedule of Assessments for this study is provided in [Appendix 1](#).

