4.6 PATIENT, TREATMENT, STUDY, AND SITE DISCONTINUATION

4.6.1 Patient Discontinuation

Patients have the right to voluntarily withdraw from the study at any time for any reason. In addition, the investigator has the right to withdraw a patient from the study at any time. Reasons for withdrawal from the study may include, but are not limited to, the following:

- Patient withdrawal of consent at any time
- Any medical condition that the investigator or Sponsor determines may jeopardize the patient's safety if he or she continues in the study
- Investigator or Sponsor determines it is in the best interest of the patient
- Patient non-compliance

Every effort should be made to obtain information on patients who withdraw from the study. The primary reason for withdrawal from the study should be documented on the appropriate eCRF. Subjects who discontinue will be asked to provide consent allowing the Study Investigator and/or F. Hoffman-La Roche Ltd to collect follow up information regarding disease progression and survival. Otherwise, without this consent, patients will not be followed for any reason after withdrawal. Patients who withdraw from the study will not be replaced.

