5.5 FOLLOW-UP OF PATIENTS AFTER ADVERSE EVENTS

5.5.1 Investigator Follow-Up

The investigator should follow each adverse event until the event has resolved to baseline grade or better, the event is assessed as stable by the investigator, the patient is lost to follow-up, or the patient withdraws consent. Every effort should be made to follow all serious adverse events considered to be related to study drug or trial-related procedures until a final outcome can be reported.

During the study period, resolution of adverse events (with dates) should be documented on the Adverse Event eCRF and in the patient's medical record to facilitate source data verification.

All pregnancies reported during the study should be followed until pregnancy outcome.

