If no baseline or post-baseline assessment is performed, patients will be censored at the start date of study treatment plus 1 day. Patients without deterioration at the time of clinical cut-off date will be censored at the last time they were known to have not deteriorated.

TTD of the pre-specified symptoms will be summarized using the Kaplan-Meier method. The median time and two-sided 95% CI for the median will also be provided.

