3.5.6 Duration of AEs

The time to resolution of specific AEs (in months) for AESI and irAE by Category will be analyzed and summarized using Kaplan Meier methodology.

- The start date will be the onset date recorded
- If AE is ongoing (no end-date), then the end date will be imputed at the cutoff date and the event will be censored.
- If a patient has ≥ 2 AE events, the worst grade will be taken into account
- If a patient has ≥ 2 AE events with the same grade, the longest will be taken into account

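### SAP 3.5.6 carries an AESI or irAE with no end date to the data cut-off even if the patient withdrew or was lost earlier, which can only lengthen the Kaplan-Meier time to resolution

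*SAP*

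**What the plan says.** SAP 3.5.6 (Duration of AEs) analyses "The time to resolution of specific AEs (in months) for AESI and irAE by Category" by Kaplan-Meier. For an event without an end date the rule is: "If AE is ongoing (no end-date), then the end date will be imputed at the cutoff date and the event will be censored". One event per patient enters. The worst grade is taken first and, among events "with the same grade, the longest will be taken into account". SAP 3.6 (Missing Data) deals with partial dates for flagging treatment-emergent events and with death dates; it adds no rule for adverse-event end dates. SAP 3 states that the SAP takes precedence over the protocol.

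Protocol 5.5.1 lists the points at which an investigator may stop following an adverse event. Besides resolution and stability they include that "the patient is lost to follow-up, or the patient withdraws consent". Under Protocol 4.6.1, patients who discontinue are asked for a further consent "to collect follow up information regarding disease progression and survival"; "without this consent, patients will not be followed for any reason after withdrawal".

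Elsewhere the SAP censors at the last informative date. OS uses the last date known alive (3.4.1.1). PFS and duration of response use the last tumor assessment (3.4.1.2, 3.4.1.5). Patients without PRO deterioration "will be censored at the last time they were known to have not deteriorated" (3.4.2).

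**The concern.** An event that is open when a patient withdraws or is lost may resolve the following week without anyone recording it. SAP 3.5.6 nevertheless counts that patient as under observation and unresolved until the cut-off. The time between last observation and cut-off is unobserved but enters the Kaplan-Meier denominator as if it had been observed.

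Protocol 3.1 names duration among the features of atezolizumab-related irAEs and SAEs to be monitored under the long-term safety objective. Results are shown by category, so some curves may rest on few patients. A plateau produced by missing follow-up could then be read as persistent toxicity.

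**Working it through.** The plan gives no figure for time to resolution, dropout or the share of open events, so there is nothing of its own to reproduce. The check has three parts.

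**1. Direction, from the rules alone.** Compare two derivations on the same data: (a) open events of withdrawn or lost patients censored at the last AE contact; (b) the SAP rule.

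- An event with an end date has the same time under (a) and (b). An open event has a time under (b) that is never shorter than under (a).
- For the choice of the longest same-grade event: suppose a patient has a resolved 3-month event and an open event observed for 1 month. Under (a) the resolved one is chosen. Under (b), with for example 10 months from onset to cut-off, the open one displaces it. The reverse cannot happen.
- So recorded resolutions can only stay or fall, and the number at risk at each time can only stay or grow. Each Kaplan-Meier factor 1 − (resolutions/at risk) can only stay or rise.

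**2. Hand example (invented data).** Ten events: six resolve at 1, 2, 3, 4, 5 and 6 months; four patients are lost at 0.5, 1.5, 2.5 and 3.5 months with the event open; cut-off at 12 months.

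- Last-contact censoring: 8/9 = 0.889; × 6/7 = 0.762; × 4/5 = 0.610; × 2/3 = 0.406; × 1/2 = 0.203; × 0 = 0. Median 4 months; 0% unresolved at 6 months.
- SAP rule: 0.9, 0.8, 0.7, 0.6, 0.5, 0.4. Median 5 months; 40% unresolved at 6 months.

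**3. Size under stated assumptions.** From the documents: median OS 13.8 months (OAK atezolizumab arm, Protocol 1.2.1.4). Assumed: exponential times; true median time to resolution of 1, 3 or 6 months; withdrawal or loss d = 0.5%, 1% or 2% per month, unrelated to resolution; one event per patient; deaths censored at death under both derivations; no outcome recorded after loss.

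Let L = ln 2/median, m = ln 2/13.8 = 0.0502 and k = L + d + m. At time t from onset, the share still observed and unresolved is exp(−kt). The share withdrawn with the event open is (d/k)(1 − exp(−kt)), and the SAP keeps these at risk. The apparent resolution hazard is therefore

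L / [1 + (d/k)(exp(kt) − 1)].

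With a = d/k, its integral is H(t) = [L/(1 − a)] × [t − ln(1 − a + a·exp(kt))/k], and the reported median solves H(t) = ln 2.

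Worked case, 3-month median and d = 0.01: L = 0.2310, k = 0.2913, a = 0.0343. At t = 3.063, exp(kt) = 2.44 and ln(1 − a + a·exp(kt))/k = 0.166, so H = 0.2393 × 2.897 = 0.693 = ln 2.

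| True median (months) | d = 0.5% | d = 1% | d = 2% | Rise |
|---|---|---|---|---|
| 1 | 1.003 | 1.007 | 1.013 | 0.3% to 1.3% |
| 3 | 3.03 | 3.06 | 3.13 | 1% to 4% |
| 6 | 6.13 | 6.28 | 6.59 | 2% to 10% |

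A simulation adding 18-month accrual, the primary cut-off and an assumed median AE onset of 2.5 months agrees to within 0.02 months. At 1% per month it carries 1.3%, 3.1% and 4.6% of 1-, 3- and 6-month events past withdrawal, adding on average 11.2, 10.1 and 9.4 unobserved months to each. Moving to the final cut-off leaves the median essentially unchanged (6.27 against 6.28 for 6-month events).

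**The case against.** **Later information may exist.** Protocol 3.1 says that after the safety period "follow-up information on disease progression (unless this has already occurred), anti-cancer therapy and survival will be collected via telephone contact", but the same paragraph adds that irAEs, SAEs and AESIs are also collected as set out in 5.4.2. Protocol 5.3.1 has investigators ask about adverse events at every patient contact. Protocol 5.5.2 lets the sponsor seek outcome information on SAEs and AESIs. A reader might infer that no outcome is ever recorded after loss; the documents do not support that. What stands is that none of these provisions gives an outcome once contact has ended, and none overrides 4.6.1 after full withdrawal.

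**The eCRF might close events at withdrawal or loss.** That would remove the problem. Completion rules are not in the documents, so it can be neither assumed nor excluded. This is why the claim is conditional.

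**The effect is small.** This stands for the median. Take 3-month events, 1% loss per month and an assumed uniform 3.5 to 21.5 months from onset to cut-off. The SAP median then differs at all from the last-contact median in about 5%, just under a fifth, and about a third of samples of 12, 30 and 60 patients. At 30 patients the mean shift is about 0.05 to 0.07 months, against a sampling range from 1.7 to over 5 months.

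**Last-contact censoring assumes that withdrawn patients resolve like the others.** If none of their events would have resolved, the SAP curve is right and last-contact censoring is too low. That is a fair limit on the size. It does not reverse the direction: the SAP rule treats these events as never resolving before cut-off, so the error is upward or nil.

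**Conclusion.** The rule as written is wrong for patients whose AE observation ended before the cut-off. Unless the eCRF supplies an end date, it counts unobserved time and can only push time to resolution upward. The direction follows from the text. The size rests entirely on assumed rates: about 0.3% to 10% on the median across the cases above, and zero if no open event belongs to a patient lost early.

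Three stronger readings do not hold.

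- A reader might infer that deaths are mishandled too. Keeping patients who died at risk to the cut-off is, without dropout, equivalent to a cumulative incidence of resolution with death competing, so no error is claimed for deaths.
- A reader might infer that reported durations will certainly be too long. The documents show only that they may be, because neither the eCRF convention nor the dropout rate is given.
- A reader might infer that the primary result is affected. Incidence of related SAEs and irAEs (Protocol 6.4, SAP 3.5.2) does not use event end dates; 3.5.6 is a supportive descriptive summary.

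Events left open because the investigator judged them stable (Protocol 5.5.1) are outside this point.

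**What to change.** In SAP 3.5.6, for patients who withdrew or were lost, censor an AESI or irAE with no end date at the earliest of withdrawal, the last contact at which AE status was assessed, and the cut-off. Count as such a contact any later contact or sponsor follow-up that recorded AE status (Protocol 3.1, 5.3.1, 5.5.2). Choose the longest same-grade event on observed time, before any end date is imputed. If the eCRF already closes events at withdrawal or loss, say so in 3.5.6 instead.

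The cost is two derivation lines and a last AE-assessment date for each patient. The downside is shorter follow-up per event, and censoring at withdrawal may itself be informative.

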5.3.3 Assessment of Severity of Adverse Events

The adverse event severity grading scale for the NCI CTCAE (v4.0) will be used for assessing adverse event severity. [Table 10](#) will be used for assessing severity for adverse events that are not specifically listed in the NCI CTCAE.

Table 10 Adverse Event Severity Grading Scale for Events Not Specifically Listed in NCI CTCAE

Grade	Severity
1	Mild; asymptomatic or mild symptoms; clinical or diagnostic observations only; or intervention not indicated
2	Moderate; minimal, local, or non-invasive intervention indicated; or limiting age-appropriate instrumental activities of daily living ^a
3	Severe or medically significant, but not immediately life-threatening; hospitalization or prolongation of hospitalization indicated; disabling; or limiting self-care activities of daily living ^{b,c}
4	Life-threatening consequences or urgent intervention indicated ^d
5	Death related to adverse event ^d

NCI CTCAE = National Cancer Institute Common Terminology Criteria for Adverse Events.

Note: Based on the most recent version of NCI CTCAE (v4.0), which can be found at:

http://ctep.cancer.gov/protocolDevelopment/electronic_applications/ctc.htm

- ^a Instrumental activities of daily living refer to preparing meals, shopping for groceries or clothes, using the telephone, managing money, etc.
- ^b Examples of self-care activities of daily living include bathing, dressing and undressing, feeding oneself, using the toilet, and taking medications, as performed by patients who are not bedridden.
- ^c If an event is assessed as a "significant medical event," it must be reported as a serious adverse event (see Section 5.4.2 for reporting instructions), per the definition of serious adverse event in Section 5.2.2.
- ^d Grade 4 and 5 events must be reported as serious adverse events (see Section 5.4.2 for reporting instructions), per the definition of serious adverse event in Section 5.2.2.

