5.3.5.4 Persistent or Recurrent Adverse Events

A persistent adverse event is one that extends continuously, without resolution, between patient evaluation timepoints. Such events should only be recorded once on the Adverse Event eCRF. The initial severity (intensity or grade) of the event will be recorded at the time the event is first reported. If a persistent adverse event becomes more severe, the most extreme severity should also be recorded on the Adverse Event eCRF. If the event becomes serious, it should be reported to the Sponsor immediately (i.e., no more than 24 hours after learning that the event became serious; see Section 5.4.2 for reporting instructions). The Adverse Event eCRF should be updated by changing the event from "non-serious" to "serious," providing the date that the event became serious, and completing all data fields related to serious adverse events.

A recurrent adverse event is one that resolves between patient evaluation timepoints and subsequently recurs. Each recurrence of an adverse event should be recorded as a separate event on the Adverse Event eCRF.

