5.3.5.8 Deaths

For this protocol, mortality is an efficacy endpoint. Deaths that occur during the protocol-specified adverse event reporting period (see Section 5.3.1) that are attributed by the investigator solely to progression of locally advanced or metastatic NSCLC should be recorded on the Death Attributed to Progressive Disease eCRF. All other deaths that occur during the adverse event reporting period, regardless of relationship to study drug, must be recorded on the Adverse Event eCRF and immediately reported to the Sponsor (see Section 5.4.2). An iDMC will monitor the frequency of deaths from all causes.

Death should be considered an outcome and not a distinct event. The event or condition that caused or contributed to the fatal outcome should be recorded as the single medical concept on the Adverse Event eCRF. Generally, only one such event should be reported. If the cause of death is unknown and cannot be ascertained at the time of reporting, "**unexplained death**" should be recorded on the Adverse Event eCRF. If the cause of death later becomes available (e.g., after autopsy), "unexplained death" should be replaced by the established cause of death. The term 'sudden death' should not be used unless combined with the presumed cause of death (e.g., "sudden cardiac death").

Deaths that occur after the adverse event reporting period should be reported as described in Section 5.6.

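### SAP 3.5.6 ignores AE outcome, so a fatal AESI or irAE that carries an end date would count as resolved; secondarily, its tie-break selects the longest episode

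*SAP*

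**What the plan says.** SAP 3.5.6 sets the endpoint and the estimator: "The time to resolution of specific AEs (in months) for AESI and irAE by Category will be analyzed and summarized using Kaplan Meier methodology". The clock starts at onset. The section has one censoring rule: "If AE is ongoing (no end-date), then the end date will be imputed at the cutoff date and the event will be censored". Two rules then reduce a patient to one record. The first is "If a patient has ≥ 2 AE events, the worst grade will be taken into account". The second covers ties: for events "with the same grade, the longest will be taken into account".

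Fatal events stay in the AE data. Protocol 5.3.5.8 states "Death should be considered an outcome and not a distinct event", and the condition that led to death is the recorded AE. The severity scale in Protocol 5.3.3, for events not listed in CTCAE, has a Grade 5 defined as "Death related to adverse event". SAP 3.5.3 tabulates AEs with a fatal outcome separately, so outcome is available for analysis.

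Repeat episodes are separate records. Protocol 5.3.5.4 says "Each recurrence of an adverse event should be recorded as a separate event on the Adverse Event eCRF", whereas a persistent event is entered once.

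Protocol 5.5.1 asks for dates of resolution on the AE form. It does not say whether a fatal AE gets an end date. SAP 3.6 covers treatment-emergent flagging and imputation of death dates, and has no rule for AE end dates or fatal outcomes. SAP section 3 says that the SAP's analyses replace those in the protocol.

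**The concern.** A missing end date is the only route to censoring. Any AE with an end date therefore becomes an event in a curve labelled time to resolution, whatever its outcome. A fatal pneumonitis closed at the date of death would enter that curve as a recovery. Where a patient has several events, the worst-grade rule would favour the Grade 5 record, so the fatal event is the one kept.

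The tie-break is a separate and smaller matter. Choosing the longest of several equal-grade episodes selects on the quantity under estimation. For those patients the curve describes the longest worst-grade episode and not a typical one.

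Protocol 3.1 names duration among the aspects by which long-term safety will be assessed, and SAP 3.5.6 is the only section that analyses it. Results are reported by category, so numbers may be small and a few deaths could visibly move a curve.

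**Working it through.** The documents give no figure for AE duration, so there is none to reproduce. The rule's logic comes from SAP 3.5.6; every numerical input below is an assumption.

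**1. Fatal events.** Let f be the fatal share of events in a category, R(t) the probability that a non-fatal event has resolved by t, and D(t) the probability that a fatal event has ended in death by t.

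- Correct share resolved by t (death as a competing event): (1 − f)·R(t)
- Share under the rule if the death date is the end date: (1 − f)·R(t) + f·D(t)
- Overstatement: f·D(t), never more than f

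Assume exponential times, a median time to resolution of 2 months and a mean time to death of 1 month. Then R(12) = 1 − 2^(−6) = 0.984 and D(12) = 1 − e^(−12), which is practically 1. For f = 5% the correct share is about 0.95 × 0.984 = 0.935, and the overstatement is close to 5 points.

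A simulation of 400,000 patients used the same assumptions, with time from onset to cutoff uniform on 6 to 24 months. At 12 months it gave:

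| Fatal share | True cumulative incidence | Death date as end date | Overstatement | No end date, censored at cutoff |
|---|---|---|---|---|
| 2% | 96.5% | 98.5% | 2.0 points | 96.5% |
| 5% | 93.6% | 98.5% | 4.9 points | 93.6% |
| 10% | 88.6% | 98.6% | 10.0 points | 88.6% |

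With no fatal events the median is 2.00 months. With the death date as end date it falls to 1.96, 1.89 and 1.80 months for the three shares. With the field blank it is 2.06, 2.15 and 2.34 months.

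The last column matches the true cumulative incidence because a patient who has died cannot resolve later. Keeping that patient at risk to an administrative cutoff is the competing-risk calculation in another form. Censoring at the date of death is not equivalent: it gave 98.4% at 12 months for all three shares.

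**2. Tied episodes.** Assume independent exponential durations with mean 1.

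- Single episode: median ln 2 = 0.693, mean 1.
- Longer of two: median −ln(1 − √0.5) = 1.228, ratio 1.228/0.693 = 1.77. The mean is 1 + 1/2 = 1.50.
- Whole curve when a share q of patients has two tied episodes: solve (1 − q)F + qF² = 0.5 with F = 1 − e^(−t). For q = 0.10, F = (−0.9 + √1.01)/0.2 = 0.525 and t = 0.744, so the ratio is 1.07.
- For q = 20%, 30% and 50% the ratios are 1.15, 1.23 and 1.39.

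Choosing an episode without regard to its length, such as the first at worst grade, returns the ratio to 1.00.

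**The case against.** SAP 3.5.6 calls the endpoint time to resolution, and Protocol 5.5.1 describes the date to be documented as one of resolution. On that reading a fatal AE never resolves, gets no end date and is censored at the cutoff, which gives the right answer. This stands in part. The documents do not settle the convention, so the error is conditional on a death date being entered. But nothing in SAP 3.5.6 or 3.6 guards against it.

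A reader might infer that both branches fail, because a dead patient is carried as unresolved to the cutoff when the field is blank. The calculation does not support this: that branch reproduces the cumulative incidence of resolution.

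A reader might also infer that durations are inflated in general. They are not. The tie-break touches only patients with two or more separate episodes at the same worst grade. Worst grade and then longest may also be a deliberate worst-case summary, and the SAP reports worst post-baseline values for laboratory data and ECOG status. That is a fair defence of keeping the rule under a clear label, but not of presenting it unlabelled as duration.

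Finally, fatal events are not hidden, since SAP 3.5.3 reports fatal AEs, deaths and causes of death. That limits the harm but does not correct the duration curve.

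**Conclusion.** The point holds as a gap in definition with a conditional error. As written, a fatal AESI or irAE with an end date would be analysed as a resolution. The overstatement at 12 months is then about the fatal share itself, 2 to 10 points for shares of 2% to 10%. Those shares and the time distributions are assumed; the documents give neither. If fatal events have no end date, the fatal-event problem does not arise.

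The tie-break is secondary. It lengthens the median 1.77 times for a patient with two tied episodes and raises the overall median by about 7% if 10% of patients have ties, under independent exponential durations.

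The two effects run in opposite directions and act on different patients, so there is no reason to expect them to cancel. Both concern a descriptive duration summary. It would be wrong to infer that the primary endpoints are affected: these are incidences of related SAEs and related irAEs (SAP 3.5.2) and use no end dates. The SAP should be corrected, but the primary results do not depend on it.

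**What to change.** In SAP 3.5.6:

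- Define the event as an end date together with a recorded non-fatal, resolved outcome.
- Treat death before resolution, whether from the AE or another cause, as a competing event and report the Aalen-Johansen cumulative incidence of resolution by category. Equivalently, keep patients who die as unresolved up to the administrative cutoff and say so. Do not censor them at the date of death.
- State how the end date of a fatal AE is to be completed, so that the result does not rest on site practice.
- Use the first episode at the worst grade as the main summary. Keep the longest episode as a sensitivity analysis labelled as worst case.

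One related detail can be settled in the same edit. Carrying an open AE to the cutoff is sound for a patient who has died, but for one who withdrew or was lost it counts unobserved time as unresolved. Those patients should be censored at last AE follow-up.

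The cost is SAP wording and, if Aalen-Johansen is chosen, a change of estimator. No new data are needed: SAP 3.5.3 already relies on fatal outcome, and Protocol 5.4 already requires changes in outcome, including recovery, to be reported for SAEs and AESIs.
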